Data from subjects and clinical readers can be obtained prospectively, or existing data can be used. An obvious difference between prospective collection of images and collection of existing images is that the clinical reader of the existing images would likely be unaware that his/her image interpretation would be used in a clinical study, whereas in prospective image reads the clinical reader would obviously be aware that his/her interpretation will be collected for the study. This will not affect the study results because the clinical interpretation would still be conducted blinded to the expert image read (which will occur after the clinical image read in every case). Indeed, similar studies of other amyloid imaging agents (Amyvid (florbetapir) and Neuraceq (florbetaben) are designed to use existing images to test clinical readers [EUPAS11867], [EUPAS12145].

Data sources will be the images and patient medical records. Image interpretations and other data will be recorded directly onto eCRFs; images will be provided electronically. All measurements are considered standard for assessment of a diagnostic test.

Each image interpretation will be compared to the corresponding majority blinded visual interpretation of 5 expert readers and sub-classified as true positive (TP), true negative (TN), false positive (FP), or false negative (FN). Expert image reads will be obtained prospectively from expert readers who consent to participate.

Diagnostic accuracy (the percentage of all images correctly interpreted) will be determined based on all images. Since the maximum possible value of diagnostic accuracy is 1, one minus the diagnostic accuracy will give the overall rate of image interpretation errors.

The standard measures of diagnostic test performance, sensitivity (TP rate for image interpretation), and specificity (TN rate for image interpretation), will also be determined based on all images. Other study endpoints will include PPV and NPV.

All of the above metrics will be determined for subsets of images by country and by reader. Further details may be found below in the body of the protocol.

Population

At least 200 VIZAMYLTM images will be collected from at least 200 subjects. Subjects will be patients who are being (or have been) evaluated for AD and other causes of cognitive impairment, who are referred (or were referred) by their physician for a clinically indicated VIZAMYLTM PET brain scan.

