Data sources

Data from subjects and clinical readers can be obtained prospectively, or existing data can be used. The clinical interpretations of existing images collected will be obtained from the patient medical record. Expert reads will be obtained prospectively from expert readers who consent to participate. Data sources will be the images and patient medical records. Image interpretations and other data will be recorded directly onto electronic case report forms (eCRFs); images will be provided to the Sponsor electronically. All measurements are considered standard for assessment of a diagnostic test.

Study size

At least 200 VIZAMYLTM images collected from at least 200 subjects will be interpreted by clinical readers from the institution where the images were obtained (i.e., each reader will interpret only those images collected at his/her institution). The readers' interpretations will be compared to the majority blinded visual interpretations of the same images made subsequently by 5 expert readers to determine diagnostic accuracy, sensitivity, specificity, PPV, and NPV.

Data analysis

Diagnostic accuracy, sensitivity, specificity, PPV, and NPV value will be determined for each reader, and reported as point estimates with exact 95% confidence intervals (CIs).

Milestones

[figure not shown]
| Milestone | Planned date |
|-------------------------------------|----------------|
| Registration in the EU PAS register | |
| Start of data collection | |
| End of data collection | |
| Final report of study results | |
| Study progress reports | Twice annually |

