| 7.0 | | | | The percentage of total number of images allowed to be contributed by individual clinical readers, institutions and countries has been changed back to the original values based on PRAC comments. Study milestones have also been updated. The option of collecting existing data has been added. |

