The efficacy of VIZAMYLTM was established in 2 pivotal clinical studies, GE067-007 and GE067-026. Both studies used histopathological analysis of brain tissue as the SOT to confirm VIZAMYLTM PET scan findings.

Study GE067-007 used 5 blinded independent readers to interpret VIZAMYLTM scans. These readers had been trained to interpret VIZAMYLTM images using an in-person training programme. Four of the readers showed high sensitivity and specificity, while the last reader showed high sensitivity but lower specificity [Curtis et al. 2015]. Analysis of reader performance resulted in recommendations for changes in the training programme, which were incorporated into an electronic training programme (ETP) which GE Healthcare developed to avoid the need for time-intensive, in-person training. The effectiveness of the ETP was evaluated in a clinical study (GE067-021) by estimating post-training sensitivity and specificity for each of 5 readers previously naïve to VIZAMYLTM image interpretation; each reader showed high sensitivity and specificity, indicating that the ETP was effective [Buckley et al. 2017].

Subsequently, GE Healthcare was asked by the EMA to analyse additional brains that had been collected but not yet analysed in Study GE067-007. This study, GE067-026, analysed data from 106 subjects for whom histopathological analyses of brain tissue were available. Five new readers were used to read the 106 images, and these readers were trained with the ETP, in contrast to Study GE067-007. This study also showed high sensitivity and specificity for all readers [Salloway et al. 2017].

Few, if any, diagnostic tests are perfect, and thus, sensitivity and specificity are rarely both 100%. This means that false-positive (FP) and false-negative (FN) results are possible. Because these inaccurate results may be acted on by physicians, FP and FN test results are potential safety issues. Image interpretation errors were thus included in the VIZAMYLTM Risk Management Plan, and the VIZAMYLTM Summary of Product Characteristics contains language recommending that all readers of VIZAMYLTM images first undergo training in the interpretation of VIZAMYLTM images.

In addition, GE Healthcare was asked by the EMA to conduct a study to determine the rate of VIZAMYLTM image interpretation errors in clinical practice and to evaluate the effectiveness of the reader training programme in Europe.

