Sensitivity, specificity, PPV, and NPV will also be calculated:

Sensitivity =
$$nTP / (nTP + nFN)$$

Specificity = $nTN / (nTN + nFP)$
 $PPV = nTP / (nTP + nFP)$
 $NPV = nTN / (nTN + nFN)$

Treatment-emergent adverse events (AEs) with onset or worsening between the start of VIZAMYLTM injection and subject discharge from the imaging suite will be recorded on an AE eCRF, along with the centre's assessment of relationship to VIZAMYLTM, severity, seriousness, timing, need for treatment, and outcome.

Study procedures for prospective data collection are summarised in the Study Schedule of Events for Prospective Data Collection (Table 2). For collection of existing data, the activities in the "Subject Enrolment" and "Imaging Visit" columns in Table 2 will have occurred in the past and may be obtained from the medical record, including whether or not the patient meets the inclusion and exclusion criteria.

 Table 2
 Study Schedule of Events for Prospective Data Collection

| Procedures | Subject Enrolment | Imaging Visit | Post- Imaging | Responsible |
|--|----------------------|------------------|------------------|-------------|
| Selection of imaging sites | | | | Sponsor |
| Informed consent obtained from subject (if IEC requires) | X | | | Centre |
| Subject inclusion/exclusion criteria assessed | X | | | Centre |
| Subject demographic information recorded | X | | | Centre |
| VIZAMYL™ administration and PET imaging; AE monitoring from start of injection until discharge from imaging centre | | X | | Centre |
| Completion of electronic case report form | | | X | |
| De-identification of subject's images | | | X | Centre |
| Transmittal of subject's images to Sponsor image core lab | | | X | Centre |
| Preparation of images for expert readers | | | X | Sponsor |

The image evaluation by expert readers will be prospective; these activities are summarised in Table 3.

Table 3 Study Schedule of Events for Image Evaluation by Expert Readers

| Procedures | Expert Selection | Expert Image Evaluation | Responsible |
|---|---------------------|-------------------------------|-------------|
| Identification of expert reader candidates | X | | Sponsor |
| Informed consent obtained from expert reader candidates | X | | Sponsor |
| Expert reader candidate inclusion/exclusion criteria assessed | X | | Sponsor |
| Selection of 5 expert readers | X | | Sponsor |
| Expert reader demographic information recorded | X | | Sponsor |

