9.2.3 Selection and Replacement of Subjects

Subjects who receive VIZAMYLTM as part of routine clinical practice will be eligible; patients scheduled for a VIZAMYLTM scan as part of a clinical study will be excluded from this study. When required by the local IEC, subjects must provide written informed consent before any study-specific data are collected. A subject will be considered enrolled in the study if he/she has provided written informed consent (if required) and any study-specific data have been collected about the subject. Subjects meeting the following criteria may be enrolled:

- 1. The subject is an adult (aged 18 years or older) of any race or gender and has been referred for a VIZAMYLTM PET brain scan as part of the assessment of his/her cognitive impairment.
- 2. The VIZAMYL™ scan was ordered as part of the clinical care of the subject and is not exclusively for a clinical trial.
- 3. If informed consent is required by the local IEC, the subject, or his/her legally authorised representative, is willing and able to sign consent for use of their de-identified VIZAMYLTM PET images and associated anatomic images (brain CT and/or MRI) used in the interpretation of the VIZAMYLTM images as well as de-identified demographic information.

Subjects must be excluded from this study if the following criterion is met:

1. If informed consent is required by the local IEC, the subject (or representative) is not willing to consent to their de-identified images and other data being used in this study.

No withdrawal criteria for this study have been formalised. In accordance with the Declaration of Helsinki, each consenting subject is free to withdraw from the study at any time. Subjects who withdraw from the study will be asked if their de-identified data may be used; if consent

to use their de-identified data is withdrawn, every effort will be made to exclude their data from analysis. Incomplete data sets from withdrawn subjects may be excluded from analysis even if permission has been granted for use if critical data are missing. Subjects whose data are excluded from analysis may be replaced.

No termination criteria for this study have been formalised. The Sponsor reserves the right to terminate the study at any time.

[figure not shown]

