9.8 Quality Control

9.8.1 Mechanisms and Procedures to Ensure Data Quality and Integrity

For eCRFs, data will be entered by trained site personnel with reasons given for any missing data. Any errors should be corrected within the electronic system. The audit trail will record all changes made, the date and time of the correction, and the person correcting the error. The appropriate electronic signature will be provided. Any data recorded directly in the eCRF, for which no other written or electronic record will be maintained in the subject's medical record, will be considered source data and should be signed by the investigator(s). Data collected from sites via eCRFs will be subject to source verification and edit checks for completeness, consistency, and logic.

GE Confidential Page 31 of 43

Audit and Inspection

The Sponsor will ensure that the analytical dataset and statistical programmes used for generating the data included in the final study report are kept in electronic format and are available for auditing and inspection.

According to International Conference on Harmonization (ICH) E6-Good Clinical Practice (GCP), the Sponsor or regulatory authorities may audit the investigational site. The Sponsor's Quality Assurance Unit, independent of the Clinical Research and Development Department, is responsible for auditing the study.

The investigator(s) must accept that regulatory authorities may conduct an inspection to verify compliance of the study with GCP.

Confidentiality Regarding Study Subjects

The investigator(s) must assure that the privacy of the subjects, including their personal identity and all other personal medical information, will be maintained at all times. In eCRFs and other documents or image material (including materials from all examinations, e.g., CT, PET, and MRI examinations) submitted to the Sponsor/CRO, subjects will not be identified by their names, but by an identification code (e.g., study subject number).

Personal medical information may be scrutinised for the purpose of verifying data recorded in the eCRF. This may be done by the monitor(s), properly authorised persons on behalf of the Sponsor, the quality assurance unit, or regulatory authorities. Personal medical information will always be treated as confidential.

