9.8.2 Source Data Verification

Source data verification will be conducted by the CRO. The monitor(s), auditor(s), authorised personnel of the Sponsor/CRO, health authority inspector(s) or their agents, and authorised members of the IECs will be given direct access to source data and documentation (e.g., medical charts/records, laboratory results, printouts, videotapes, etc.) for source data verification, provided that subject confidentiality is maintained in accordance with local requirements. Image evaluation data from the clinical readers and expert readers will be entered directly into the eCRF and so no source verification is required.

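### Section 9.8.2 exempts all clinical reads from source verification on a ground that fails for existing reads taken from the medical record, and so contradicts Sections 9.8.1 and 9.6.2

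*Protocol*

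**What the plan says.** **Verification.** Protocol Section 9.8.2 gives source data verification to the CRO and gives monitors access to charts. It then exempts the reads: "Image evaluation data from the clinical readers and expert readers will be entered directly into the eCRF and so no source verification is required". It does not separate existing from prospective clinical reads.

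Section 9.8.1 sets the test for treating the eCRF itself as source. This applies to data entered there "for which no other written or electronic record will be maintained in the subject's medical record, will be considered source data". The same section puts eCRF data from sites under source verification, and Section 9.6.2 lists source data verification among the monitoring methods.

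**Existing data.** Section 5 records under version 7.0: "The option of collecting existing data has been added". Section 9.4.1 permits existing data and sets no limit on their share. The abstract (Data sources) states: "The clinical interpretations of existing images collected will be obtained from the patient medical record". Section 9.1.1 adds that the enrolment and imaging items for such subjects "may be obtained from the medical record, including whether or not the patient meets the inclusion and exclusion criteria".

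**Choice of scans.** Section 9.2.3 is permissive: "Subjects meeting the following criteria may be enrolled". Section 9.2.4 requires that an image be interpretable and transferred. Section 9.2.5 caps each reader at 7.5%, each institution at 15% and each country at 25% of images. Section 9.9 names two limitations: coverage of countries and sites, and how representative the readers are.

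**Reporting.** SAP Sections 8.6.2 and 8.6.3 report accuracy, and the certainty of the clinical reader and of the standard of truth (SOT), for prospective, retrospective and pooled images.

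**The concern.** The clinical read is the index result. Compared with the expert majority, it places each image in the TP, TN, FP or FN cell, and every primary endpoint follows from those four counts. For existing images this field is copied from a record, yet it is the field excused from checking. Section 7 says that the EMA asked for the rate of "image interpretation errors in clinical practice and to evaluate the effectiveness of the reader training programme in Europe". A copying error would be counted as a reader's error.

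The abstract's argument that existing images are harmless covers only reader awareness and blinding: "This will not affect the study results because the clinical interpretation would still be conducted blinded to the expert image read". It does not address transcription, nor which scans are chosen.

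The second, lesser matter is choice. If a reader or site has more eligible existing scans than its cap allows, some must be left out, and neither document says how.

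**Working it through.** **1. The waiver's reason, by type of read**

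- Expert reads are always prospective, so direct entry applies and the reason holds.
- Prospective clinical reads are entered by the reader into the eCRF (Section 9.1.1). The reason holds where the eCRF is the first record.
- Existing clinical reads are taken from the medical record (abstract). The eCRF entry is a copy, so the reason fails. By the test in Section 9.8.1 the record is the source, because another record exists.

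For existing reads, then, 9.8.2 says that no verification is needed, while 9.8.1 and 9.6.2 say that site data are verified. The passages must be reconciled.

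**2. The plan's own precision figure**

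Inputs from Section 9.5: 200 subjects and 90% accuracy, so 180/200 correct. The Clopper-Pearson limits are the 2.5% quantile of Beta(180, 21) and the 97.5% quantile of Beta(181, 20). These are 84.98% and 93.78%, a width of 8.81 points. The stated width of less than 10% is reproduced. The half-width is 8.81/2 = 4.4 points.

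**3. Effect of transcription error**

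Let a = true accuracy (90%, Section 9.5), e = the proportion of existing reads whose positive/negative result is miscopied, and f = the share of existing images. The documents give neither e nor f, so both are assumptions. The errors are taken to be unrelated to the expert read.

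- Observed accuracy in existing images = a(1 − e) + (1 − a)e = 0.9 − 0.8e
- Pooled accuracy = f(0.9 − 0.8e) + (1 − f)0.9 = 0.9 − 0.8ef

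Fall in pooled accuracy, in percentage points:

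| | f = 25% | f = 50% | f = 100% |
|---|---|---|---|
| e = 1% | 0.2 | 0.4 | 0.8 |
| e = 2% | 0.4 | 0.8 | 1.6 |
| e = 5% | 1.0 | 2.0 | 4.0 |

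At e = 1% and f = 50%, 200 × 0.5 × 0.01 = 1 read is miscopied and a 10% error rate is reported as 10.4%. At e = 2% and f = 100%, 4 reads are miscopied and 10% becomes 11.6%. Every entry in the table is below 4.4 points. The direction is downward because a exceeds 50%.

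The formula measures all transcription error. Verification removes only what it catches, so these figures are an upper limit on the benefit of the fix.

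**4. Choice of scans**

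With 200 images the reader cap is 0.075 × 200 = 15. A reader with more than 15 eligible existing scans would have to leave some out. The documents give no count of eligible scans per reader and no measure of preference, so the size of any selection effect cannot be calculated from them.

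**The case against.** **Verification is required elsewhere.** A reader might infer that nothing obliges anyone to check existing reads. The documents do not support that. Sections 9.8.1 and 9.6.2 state a general rule, and the waiver is tied to direct entry, so transcribed reads could be held to fall outside it. A Data Management Plan (Section 9.6.5), not part of these documents, may say more. What remains is that 9.8.2 is the specific provision and its wording covers all clinical reads. The fault is a contradiction, not the absence of any requirement.

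**The effects are small.** This is correct for every case shown, and the 4.0-point case needs 5% miscopying of a binary field with all images existing. But the error is a bias: the exact interval does not reflect it and more images would not remove it.

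**Selection is limited and partly detectable.** A reader might infer that sites could favour scans that were read correctly. Expert reads come after the clinical read and sites are blinded to them, so that route is closed. A preference for visually clear scans needs no such knowledge. A reader might also infer that such a preference, which raises accuracy, could be cancelled by transcription error and go unseen. That holds for accuracy alone. SAP Sections 8.6.2 and 8.6.3 also split SOT certainty, and accuracy by SOT certainty, into prospective and retrospective images. SOT certainty comes from the experts, so miscopied clinical reads cannot alter it, and a preference for clear scans should show as higher certainty in retrospective images. This detects and does not prevent, and it needs enough prospective images for comparison.

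**The caps may not bind.** Section 9.5 expects very few scans per reader at some institutions, and no document shows a reader with more eligible existing scans than the cap.

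**Conclusion.** The main point stands and should be corrected. As written, the waiver in 9.8.2 is wrong for existing clinical reads and conflicts with 9.8.1, 9.6.2 and the abstract. This rests on the text and needs no assumption.

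The size does rest on assumptions: the error rate, the existing share, independence from the expert read, and the plan's 90% accuracy. Within the ranges shown, the pooled fall runs from 0.2 to 4.0 points, always below the sampling error. The primary estimate is not shown to be invalid. The case for change is that the field is decisive and the check is cheap.

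The missing selection rule is a real gap but of lower severity. No size can be attached to it, and the caps are not shown to bind.

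**What to change.** **Main change.** In Section 9.8.2, limit the waiver to expert reads and to clinical reads first recorded in the eCRF. Have the CRO verify each existing clinical read against the original dated report.

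**Secondary change.** In Sections 9.2.3 to 9.2.5, state how existing scans are chosen when more are eligible than the cap allows. The rule should take no account of image content or the recorded read, for example consecutive scans from a fixed date or a random draw. A most-recent-first rule may thin the category of less than 6 months from training, which is a secondary variable. Report the number of eligible scans not included, as far as consent rules allow, and add image selection to Section 9.9.

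**Cost.** A short protocol amendment with ethics committee review (Section 9.10) and, judging by the version history in Section 5, possibly PRAC review. The CRO already performs source verification. The added work is one field per existing image: about 100 checks if half of 200 images are existing, 200 if all are. Counting omitted scans is a small task for each reader or site. Where consent is required a complete consecutive series may not be attainable, so omitted scans should be counted and not forbidden.
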